4.2 General Statistical Methods and Data Handling

4.2.1 General Methods

Tabulations will be produced by enrollment group (PRN Dosing (2-8), PRN Dosing (9-14), EOD+PRN Dosing (4-14)) and overall, unless specified otherwise. Note that “enrollment group” refers to the dosing groups assigned at screening based on migraine history during the 3 months prior to the Screening Visit (see Sections 2.1 and 2.2). The “PRN Dosing (2-8)” enrollment group will include subjects with a history of 2-8 moderate to severe migraines per month receiving rimegepant PRN for 52 weeks (i.e., “52-week PRN (2-8)”) and subjects receiving rimegepant PRN with FDA-approved CGRP antagonist biologics for 12 weeks (i.e., “12-week PRN (2-8)”).

Refer to the BHV3000 Core SAP for descriptive statistics, counting rules, rounding rules, dictionaries for coding AEs, medical history, and non-study medications, and examples of complete dates.

See Section 5 for conventions.

4.2.2 Computing Environment

All statistical analyses will be performed using SAS statistical software (Version 9.4 or higher).

4.2.3 Methods of Pooling Data

Enrollment groups are pooled for analysis of endpoints of interest by all subgroups of interest (see Section 4.2.6).

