Patients in the every other day dosing group (history of 4-14 moderate to severe migraines/month) will be instructed that they must take one tablet of rimegepant every other calendar day, regardless of whether or not the patient has a migraine. If patients in this group have a migraine on a day that they are not scheduled to dose with rimegepant, they may take a rimegepant tablet to treat a migraine of mild, moderate or severe intensity. Therefore, patients in this group can take a maximum of one tablet of rimegepant per calendar day for up to 12 weeks.

Patients are required to record their migraine occurrence and severity and all study medication doses in the eDiary and are required to continue to record the standard of care migraine treatment taken on a paper diary. Patients will also use the eDiary to complete

the Preference of Medication (PoM) questionnaire and the Satisfaction with Medication (SM) questionnaire at specified study timepoints.

At select study visits, patients will complete or will be administered the Migraine-specified Quality-of-Life Questionnaire v 2.1 (MQoLQ), the Migraine Disability Assessment (MIDAS), Clinical Global Impressions-change (CGI-c) scale, and the Sheehan Suicidality Tracking Scale (S-STS) on paper forms, at specified study visits.

Additional assessments and visit schedule are outlined in the procedural table in Section 4.3. Procedures include study personnel review of the eDiary and paper diary with the patient, assessment of study medication compliance, monitoring of tolerability and safety (including vital signs, laboratory tests, and electrocardiography). Study visits will be approximately every two weeks during the first month and then every 4 weeks until Week 52 for subjects in the 2-8 moderate to severe migraine/month group or the 9-14 moderate to severe migraine/month group.

Study visits will be approximately every two weeks during the first month and then every 4 weeks until Week 12 for subjects in the every other day dosing group (those with history of 4-14 moderate to severe migraines/month).

Patients will return to the study site at the end of Week 52 (or Week 12 for subjects in the every other day dosing group (history of 4-14 moderate to severe migraines/month)) (+/-7 days) for the End of Treatment Visit. There is a Follow-up Visit 14 days (+/-2 days) after the Week 12/52/EOT Visit.

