#### 7.2.2 Selection and Timing of Dose and Administration

Study medication (rimegepant) will be assigned via the IWRS. There are no dose adjustments in this study and patients will receive 30 tablets of rimegepant in a bottle. Patients will be dispensed study medication at the Baseline Visit, and the patients in the 2-8 and 9-14 moderate to severe migraines per month groups will be instructed that they can take the one tablet of study medication per calendar day at the onset of a migraine of mild to severe intensity. Patients in the in the 2-8 and 9-14 moderate to severe migraines per month groups will dose for up to 52 weeks.

Patients in the 4-14 moderate to severe migraine group will also be dispensed study medication at the Baseline Visit and will be instructed to dose with one rimegepant tablet every other calendar day, regardless of whether they have a migraine on that day or not. If the patients in this group have a migraine (mild to severe intensity) on a non-dosing day, they may take a rimegepant tablet, for a maximum of one tablet per calendar day. Patients in the 4-14 moderate to severe migraines per month group will dose for up to 12 weeks.

Dosing of study medication is not to occur until after eligibility is confirmed based on the subject's baseline laboratory tests.

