4.2.6 Subpopulations

The subgroups of interest for this study are the following:

- Intrinsic factors
 - Age: categorized as < 40, \geq 40, < 65, \geq 65
 - Sex: female, male
 - Sex and age: female < 40, female \geq 40, male < 40, male \geq 40
 - Race: white, black or African American, other including Asian, Asian
 - Ethnicity: Hispanic or Latino, not Hispanic or Latino
- Extrinsic disease-related factors
 - CV risk contraindicating triptans: yes, no (see Section 5.2.2)
 - Baseline body mass index (BMI; kg/m²): categorized as < 25, \geq 25 to < 30, \geq 30
 - Prophylactic migraine medication use on or after study drug start: yes, no (see Section 4.9)
- Extrinsic exposure factors
 - Time on rimegepant (weeks): categorized as quintiles for treated subjects (see Sections 4.8.1 and 5.2.3)

- Cumulative rimegepant exposure (tablets): categorized as quintiles for treated subjects (see Sections 4.8.1 and 5.2.3)
- Key factors
 - Average rimegepant exposure (tablets per 4 weeks): categorized as < 2, ≥ 2 to < 8, ≥ 8 to < 14, ≥ 14 for treated subjects (see Section 4.8.1)
 - Average rimegepant exposure (tablets per 4 weeks) for EOD+PRN treated subjects: categorized as < 14, ≥ 14 (see Section 4.8.1)
 - Treated subjects who took ≥ 14 tablets per 4 weeks for ≥ 12 weeks: categorized by enrollment group (see Section 4.8.1)
 - Treated subjects who took ≥ 20 tablets per 4 weeks for ≥ 4 weeks: categorized by enrollment group (see Section 4.8.1)
 - Treated subjects with near-daily dosing, defined as those in the (1) PRN dosing groups who took ≥ 14 tablets per 4 weeks for ≥ 12 weeks (see previous bullet), or (2) EOD+PRN dosing group: categorized by enrollment group.

Subgroup levels may be combined or redefined based on the availability of the data.

Subgroup tabulations will be by subgroup level and overall for treated subjects with non-missing subgroup level data. Refer to the BHV3000 Core SAP for rounding rules.

The triptan non-responder (yes, no) subgroup will be derived according to Section 5.2.1, included in the subgroup summary table (see Section 4.5), and excluded from subgroup tabulations by subgroup level and overall.

4.2.7 *Withdrawals, Dropout and Loss to Follow-Up*

Subjects who withdrew from the study were not replaced.

4.2.8 *Missing, Unused and Spurious Data*

Analyses will be based on observed data only.

4.3 *Planned Analyses*

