4.6.3 Exploratory Safety and Other Endpoints

4.6.3.1 LFT Elevations

The number and percentage of subjects with LFT elevations will be summarized separately for the following populations and safety analysis periods:

- Screened subjects during pre-treatment by enrollment group, and overall
- Treated subjects during pre-treatment by enrollment group and overall
- Treated subjects on-treatment by enrollment group and overall
- Treated subjects on-treatment by subgroup level and overall for all subgroups of interest specified in Section 4.2.6
- Treated subjects on-treatment by enrollment group and overall for subjects who did not participate in previous Studies BHV3000-301/302/303
- Follow-up subjects during follow-up by enrollment group and overall.

LFT elevations include the following endpoints:

- Cumulative elevations:
 - ALT $> 1 \times, > 3 \times, > 5 \times, > 10 \times$, and $> 20 \times$ ULN
 - AST $> 1 \times, > 3 \times, > 5 \times, > 10 \times$, and $> 20 \times$ ULN
 - ALT or AST $> 1 \times, > 3 \times, > 5 \times, > 10 \times$, and $> 20 \times$ ULN
 - TBL $> 1 \times, 1.5 \times$, and $> 2 \times$ ULN
 - Alkaline phosphatase (ALP) $> 1 \times, > 1.5 \times$, and $> 2 \times$ ULN

- Mutually exclusive elevations:
 - ALT > ULN to $\leq 3 \times$ ULN, $> 3 \times$ ULN to $\leq 5 \times$ ULN, $> 5 \times$ ULN to $\leq 10 \times$ ULN, $> 10 \times$ ULN to $\leq 20 \times$ ULN, and $> 20 \times$ ULN
 - AST > ULN to $\leq 3 \times$ ULN, $> 3 \times$ ULN to $\leq 5 \times$ ULN, $> 5 \times$ ULN to $\leq 10 \times$ ULN, $> 10 \times$ ULN to $\leq 20 \times$ ULN, and $> 20 \times$ ULN
 - ALT or AST > ULN to $\leq 3 \times$ ULN, $> 3 \times$ ULN to $\leq 5 \times$ ULN, $> 5 \times$ ULN to $\leq 10 \times$ ULN, $> 10 \times$ ULN to $\leq 20 \times$ ULN, and $> 20 \times$ ULN
- Composite elevations:
 - ALT or AST $> 3 \times$ ULN and TBL $> 1.5 \times$ ULN
 - ALT or AST $> 3 \times$ ULN and TBL $> 2 \times$ ULN
 - ALT or ALT $> 3 \times$ ULN concurrent with TBL $> 2 \times$ ULN with Agresti-Coull 95% CIs (see Section 4.6.2)
 - ALT or ALT $> 3 \times$ ULN concurrent with TBL $> 2 \times$ ULN and ALP $\leq 2 \times$ ULN with Agresti-Coull 95% CIs (see Section 4.6.2)
 - ALT or AST $> 3 \times$ ULN concurrent with AEs of interest (nausea, vomiting, anorexia, abdominal pain, fatigue; see Section 4.6.3.2).

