5.2.3 Rimegepant Exposure

Rimegepant exposure subgroups are derived from parameters defined in Section 4.8.1 as follows:

- Time on rimegepant subgroups are based on quintiles of total weeks on treatment (< P20, ≥ P20 to < P40, ≥ P40 to < P60, ≥ P60 to < P80, ≥ P80) based on eDiary for treated subjects pooled across enrollment group. Percentiles will be rounded to 1 decimal place.
- Cumulative rimegepant exposure subgroups are based on quintiles of the total number of study drug tablets taken (< P20, ≥ P20 to < P40, ≥ P40 to < P60, ≥ P60 to < P80, ≥ P80) based on eDiary for treated subjects pooled across enrollment group. Percentiles will be rounded to integers.
- Average rimegepant exposure subgroups are based on average rimegepant exposure (tablets per 4 weeks), which is calculated as 4*cumulative rimegepant exposure/time in the LTT period for treated subjects pooled across enrollment group.

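### Event percentages by average tablet use mix 12-week and 52-week treatment, so excess risk at the highest intensity can be diluted or, above roughly a two-thirds 12-week share, reversed

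*SAP*

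**What the plan says.** SAP 4.2.3 sets the pooling rule: "Enrollment groups are pooled for analysis of endpoints of interest by all subgroups of interest". SAP 4.2.6 lists among the key factors "Average rimegepant exposure (tablets per 4 weeks): categorized as < 2, ≥ 2 to < 8, ≥ 8 to < 14, ≥ 14". SAP 5.2.3 repeats the pooling for this measure, "which is calculated as 4*cumulative rimegepant exposure/time in the LTT period for treated subjects pooled across enrollment group".

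The pooled groups have different treatment lengths. Protocol 7.2.2 says that patients in the "2-8 and 9-14 moderate to severe migraines per month groups will dose for up to 52 weeks", and for the every-other-day group: "Patients in the 4-14 moderate to severe migraines per month group will dose for up to 12 weeks". The latter are "instructed to dose with one rimegepant tablet every other calendar day, regardless of whether they have a migraine on that day or not", and may take as-needed tablets on the other days. Visits follow the same split: every two weeks in the first month, "then every 4 weeks until Week 12 for subjects in the every other day dosing group" (Protocol 4.1).

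The liver-test tables give numbers and percentages of subjects, including "Treated subjects on-treatment by subgroup level and overall for all subgroups of interest specified in Section 4.2.6" (SAP 4.6.3.1). The adverse-event tables by subgroup (SAP 4.8.2) and the hepatic endpoints by exposure (SAP 4.6.3.4 and Table 3) take the same form. SAP 4.8.2 lists exposure-adjusted adverse-event and serious-event tables without the mark that would repeat them by subgroup. SAP 4.6.3.1 describes the exposure-adjusted liver-test table for treated subjects, with no breakdown by exposure. SAP 4.2.4 plans no covariate adjustment or stratification.

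**The concern.** A crude percentage of patients with an event rises with time under observation. If one intensity band holds many patients observed for 12 weeks and another holds patients observed for up to 52, the contrast between bands mixes intensity with duration. Every-other-day dosing puts 12-week patients at or near the top band, so the expected direction of the bias is toward reassurance about the most intensive use.

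The contribution of rimegepant exposure to liver-test abnormalities is an exploratory objective. SAP Table 3 also names average exposure as one of the breakdowns for hepatic serious events, hepatic discontinuations and concurrent elevations. A flat or falling pattern across the four bands could be read as absence of a dose relation when it partly reflects shorter follow-up. The eDISH plot by average exposure has the same weakness, because each patient's maximum is taken over fewer draws in the 12-week group.

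**Working it through.** **1. The plan's own figures.** The documents give no figure for the pooled exposure tables. The zero-event bounds in Protocol 9.2 and SAP 4.1 reproduce: 1 − 0.05^(1/2000) = 0.001497 and 1 − 0.05^(1/800) = 0.003738, against 0.0015 and 0.00375. They do not bear on this point. SAP 4.8.1 gives 12.6 tablets per 4 weeks as 90% every-other-day compliance and 11.2 as 80%. Both imply 12.6/0.90 = 11.2/0.80 = 14, which is the lower edge of the top band.

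**2. Inputs from the documents.**
- Planned treatment: 12 against 52 weeks (Protocol 7.2.2).
- Scheduled on-treatment liver tests: Weeks 2, 4, 8 and 12, so 4 draws, against Weeks 2, 4 and 8 to 52 every four weeks, so 14 draws (Protocol Tables 1 and 2).
- Planned numbers: about 200 every-other-day and 1200 + 600 = 1800 as-needed patients (Protocol 5).

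**3. Assumptions.** The share s of 12-week patients in the top band is not given and is shown as a range. The base case has a constant hazard, rare events, no dropout, and a comparison band made up wholly of 52-week patients.

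**4. Apparent ratio.** For a true hazard ratio HR in the top band, the crude ratio is R = HR × [s × 12/52 + (1 − s)] = HR × [1 − s × 40/52].

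| s | R at HR = 1 | R at HR = 2 |
|---|---|---|
| 0% | 1.00 | 2.00 |
| 25% | 0.81 | 1.62 |
| 50% | 0.62 | 1.23 |
| 65% | 0.50 | 1.00 |
| 75% | 0.42 | 0.85 |
| 90% | 0.31 | 0.62 |
| 100% | 0.23 | 0.46 |

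A doubling reads as equality when 1 − s × 40/52 = 0.5, so s = 0.65. If 160 of the 200 every-other-day patients were in the top band, that share would correspond to 160 × 0.35/0.65 = 86 as-needed patients there, or 86/1800 = 4.8% of them. With fewer, a doubling would look lower.

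**5. As percentages, taking a 52-week risk of 2%.** The 12-week risk is 1 − 0.98^(12/52) = 0.465%. At equal hazard the top band shows 1.23%, 0.85% or 0.62% for s = 50%, 75% or 90%, against 2.0%. At HR = 2 the component risks are 1 − 0.98^(24/52) = 0.928% and 1 − 0.98² = 3.96%. The top band then shows 0.5 × 0.928 + 0.5 × 3.96 = 2.44% at s = 50%, and 0.75 × 0.928 + 0.25 × 3.96 = 1.69% at s = 75%.

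**6. Sensitivity of the turning point for a doubling.**
- On-treatment window including the 7 days after last dose (13 against 53 weeks): 0.5 × 53/40 = 66%.
- As-needed follow-up averaging 40 weeks: 0.5 × 40/28 = 71%.
- Comparison band itself 25% 12-week patients: at s = 75%, R = 2 × (1 − 0.75 × 40/52)/(1 − 0.25 × 40/52) = 2 × 0.423/0.808 = 1.05. Dilution remains but there is no reversal.
- Early-clustering events (Weibull shape k): at s = 75%, reversal ends when 0.75 × (12/52)^k + 0.25 = 0.5, so k = ln 3/ln(52/12) = 0.75. At s = 100%, k = ln 2/ln(52/12) = 0.47. Below these shapes a doubling still looks higher.

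**7. Possible make-up of the bands.** A grid of 27 assumed settings varied every-other-day adherence (80%, 90%, 98%), as-needed use on non-dosing days (none, half, full) and tablets per attack (0.7, 1.0, 1.3). The 12-week share of the top band ran from 1% to 98%. The top band had the shortest mean planned follow-up in 22 of 27 settings. A doubled hazard there looked lower than in the 2 to < 8 band in 13, and lower than in the 8 to < 14 band in 11. The five exceptions on follow-up all had adherence of 90% or less and no as-needed use; in those, the apparent ratio against the 8 to < 14 band was above 2.

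**The case against.** A reader might infer that the top band must have the shortest follow-up and that a doubled risk will therefore look lower. The documents do not support that. Fourteen is only the lower edge: perfect every-other-day dosing over 84 days is 42 tablets, and one missed tablet without as-needed use gives 41 × 4/12 = 13.7, which falls in 8 to < 14. A day with no eDiary drug entry counts as no tablet (SAP 4.8.1), which lowers averages further. As-needed patients with 9-14 attacks a month may also treat mild ones, so some may reach 14. The lower bands are therefore not purely 52-week patients. About 20 as-needed patients on CGRP biologics are also treated for only 12 weeks (SAP 2.1). All of this stands, and it limits the claim to an expected direction.

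Nor do the documents call this factor the main look at intensity; it is one of five key factors. The SAP also has partial safeguards:
- the every-other-day group is split at 14 on its own, at equal planned duration;
- the subgroups for 14 or more tablets over 12 weeks, 20 or more over 4 weeks, and near-daily use are shown by enrollment group;
- time on drug is tabulated by subgroup (SAP 4.8.1);
- elevations per liver test are summarized by key factor (SAP 4.6.3.1).

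These reveal the imbalance or avoid it in part. They do not correct the four-band tables. The within-group split has no low-use comparator, the by-group subgroups are not a low-to-high gradient, and the per-test rate does not cover adverse events, serious events or hepatic events.

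Finally, the study is single-arm and descriptive (Protocol 9.4). That lowers the stakes, but a descriptive table can still mislead.

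**Conclusion.** The point holds in a conditional form. Pooling, unequal planned duration, crude percentages and the absence of exposure-adjusted tables by band are all explicit in the documents. The top band is expected to have a larger 12-week share and shorter follow-up than the lower bands. Under constant hazard and a 52-week comparator, a true doubling shows as about 1.2 at a 50% share, 1.0 at 65% and 0.85 at 75%: diluted below roughly two-thirds, reversed above.

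The size rests on an unknown share, on how many every-other-day patients fall in 8 to < 14, on as-needed dropout, and on whether events cluster early. Each of the last three, in the direction discussed, makes reversal less likely. A general claim that the highest intensity will look safest goes beyond the documents. The point concerns only the four-band adverse-event, serious-event, hepatic-event and liver-test outputs, not the tables by enrollment group. It should be fixed because the change is small.

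**What to change.** 1. For the average-exposure factor, add a version of the adverse-event, serious-event, hepatic-event and liver-test tables in which both the exposure band and the events use only treatment weeks 1-12 in all subjects. Every group then has the same scheduled draws at Weeks 2, 4, 8 and 12. The cut-off rule should be identical across groups and late enough to keep the Week 12 draw, whose window ends on study day 98 in both SAP Table 5 and Table 6.
2. Extend the exposure-adjusted adverse-event, serious-event and liver-test tables to this factor.
3. Keep the full-period percentages, with a footnote that the bands differ in treatment duration.

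The cost is a few extra tables from derivations that the SAP already has. Neither addition is enough alone. The 12-week version says nothing about late events. Person-time rates assume a roughly constant hazard and can overstate risk in a band with many 12-week patients when events cluster early: at equal hazard and Weibull shape 0.5, an all-12-week band would show a rate ratio of about (12/52)^0.5/(12/52) = 2.1. The two should be read together.

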4.2.4 Adjustments for Covariates and Stratification

This is not applicable to this study.

4.2.5 Multiple Comparisons

This is not applicable to this study.

4.2.6 Subpopulations

The subgroups of interest for this study are the following:

- Intrinsic factors
 - Age: categorized as < 40, \geq 40, < 65, \geq 65
 - Sex: female, male
 - Sex and age: female < 40, female \geq 40, male < 40, male \geq 40
 - Race: white, black or African American, other including Asian, Asian
 - Ethnicity: Hispanic or Latino, not Hispanic or Latino
- Extrinsic disease-related factors
 - CV risk contraindicating triptans: yes, no (see Section 5.2.2)
 - Baseline body mass index (BMI; kg/m²): categorized as < 25, \geq 25 to < 30, \geq 30
 - Prophylactic migraine medication use on or after study drug start: yes, no (see Section 4.9)
- Extrinsic exposure factors
 - Time on rimegepant (weeks): categorized as quintiles for treated subjects (see Sections 4.8.1 and 5.2.3)

- Cumulative rimegepant exposure (tablets): categorized as quintiles for treated subjects (see Sections 4.8.1 and 5.2.3)
- Key factors
 - Average rimegepant exposure (tablets per 4 weeks): categorized as < 2, ≥ 2 to < 8, ≥ 8 to < 14, ≥ 14 for treated subjects (see Section 4.8.1)
 - Average rimegepant exposure (tablets per 4 weeks) for EOD+PRN treated subjects: categorized as < 14, ≥ 14 (see Section 4.8.1)
 - Treated subjects who took ≥ 14 tablets per 4 weeks for ≥ 12 weeks: categorized by enrollment group (see Section 4.8.1)
 - Treated subjects who took ≥ 20 tablets per 4 weeks for ≥ 4 weeks: categorized by enrollment group (see Section 4.8.1)
 - Treated subjects with near-daily dosing, defined as those in the (1) PRN dosing groups who took ≥ 14 tablets per 4 weeks for ≥ 12 weeks (see previous bullet), or (2) EOD+PRN dosing group: categorized by enrollment group.

Subgroup levels may be combined or redefined based on the availability of the data.

Subgroup tabulations will be by subgroup level and overall for treated subjects with non-missing subgroup level data. Refer to the BHV3000 Core SAP for rounding rules.

The triptan non-responder (yes, no) subgroup will be derived according to Section 5.2.1, included in the subgroup summary table (see Section 4.5), and excluded from subgroup tabulations by subgroup level and overall.

4.2.7 *Withdrawals, Dropout and Loss to Follow-Up*

Subjects who withdrew from the study were not replaced.

4.2.8 *Missing, Unused and Spurious Data*

Analyses will be based on observed data only.

4.3 *Planned Analyses*

During the course of this study, laboratory, safety and exposure data will be monitored on an ongoing basis. The analyses planned for endpoints that use data from this study may be conducted after an interim database lock, prior to last patient last visit. The CSR will be produced after last patient last visit and final database lock.

